6.3 Modification of Study Product for a Subject

There is no dose adjustment for the product in the study.

6.4 Accountability Procedures for Study Product

The study vaccine and placebo will be kept in a secure place, in cold storage, and segregated from other products at the study clinic. During the study, the investigator or the person in charge of research product management will record information related to the delivery of vaccine and placebo to the trial site, conduct inventory at the trial site, check the number of doses given to the participants, check the number of unused doses, and return the unused doses to IVAC upon completion of the study.

At the Vaccination Site

- On scheduled vaccination days, study vaccine and placebo will be transported to the local site with proper temperature control and monitoring.
- Standard procedures will be followed at the trial site to maintain proper transport, receipt, storage, and return of study products.
- In the case of interruption of the cold chain (i.e., the temperature is out of acceptable range), the Principal Investigator or qualified designated staff member must contact IVAC to get further instructions. The investigator must receive written consent (through facsimile or emailed scanned copy) from IVAC before clinical trial products can be used.

6.5 Assessment of Compliance with Use of the Study Products

Compliance with use of the study products will be closely monitored during the trial by the research team, IVAC, and trial monitors.

6.6 Concomitant Medications/Treatment

Concomitant medications will be documented through Day 43 of the study and then at Day 91 only for medications taken for SAEs.

Treatment of conditions that are not exclusionary should continue, if needed by the subject. Subsequent changes in concomitant treatment during the trial must also be reflected in the CRF.

Women included in the trial who are using hormonal contraception for pregnancy prevention should continue taking these products during the entire trial. Use of such products must also be documented in the CRF.

6.7 Unauthorized Products

The following products are not authorized to be used during the study:

1. Any concomitant medicine or biologic specifically prescribed for the treatment of a condition which is an exclusion criterion for participation in the trial.
2. All non-study vaccines or biologics (including blood products).

Other concomitant medications will be reviewed on a case-by-case basis if the study staff are unclear.

Subjects will be requested not to take analgesic or antipyretic drugs *in a preventive way* (before or soon after injection), as such medications might change the reactogenicity profiles of study vaccine and placebo.

During the trial, if a situation arises where there is an adverse reaction or AE requiring treatment and prescription of unauthorized products or products not stipulated by the protocol, then such products may be prescribed. However, IVAC must be informed of such an occurrence within 48 hours. Information on the products (trade name, dosing or change in dosing, indications, start date, and termination date) must be recorded in the CRF.

7 Study Schedule; Description of Visits

The total expected duration of the study:

First subject enrolled in study	Day 1 of first subject
The last subject enrolled in study	For Phase 2: Day 1 of last subject is estimated 2-4 weeks from Day 1 of first subject; Phase 3: Day 1 of last subject is estimated approximately 18 months after the Day 1 of first subject from Phase 2.
The last subject completes the trial	Day 91 of last subject
Lock database	8 weeks after Day 91 of last subject for each Phase
Clinical trial report	8-10 months after Day 91 of last subject for Phase 3

7.1 Screening: Phase 2 Subjects

Prior to inclusion into the vaccine study, each subject will be screened by laboratory testing, medical history interview, and physical examination. Because screening procedures are required to assess eligibility, they will be performed under a screening informed consent form (ICF A) for Phase 2 subjects prior to the subject providing informed consent for study participation (ICF B). The investigator will record the screening IDs of all participants who enter screening; whether they entered the trial or failed screening, and the reason for screen failure on the screening/enrollment log.

7.1.1 First Screening Visit (Day S1)—Phase 2

The first screening visits can occur from 30 days to 3 days before S2/D1.

After subjects are consented into the screening process (using ICF A), the following activities will occur:

1. The subject will be interviewed to collect baseline demographic data.
2. A study clinician will interview the subject to collect a detailed medical history, focusing on current medical conditions. Study staff will review the information to confirm eligibility prior to conduct of further procedures.
3. A study clinician will perform a general physical examination. Results will be reviewed by study staff and with the subject to confirm eligibility prior to conduct of further procedures. If a person is considered ineligible based on medical history and physical examination, the study clinician will tell the person that he or she is not eligible; however, if they would like, the study can conduct the laboratory screening tests and provide results to them or their regular physician.
4. Blood (serum and whole) specimens will be collected for biochemical and hematological testing. Serum specimens will also be collected for testing for chronic viral hepatitis infections. Specimen collection information must be documented in appropriate source documents/CRFs.
5. For women able to become pregnant, a urine pregnancy test will be done.
6. Study staff will instruct the subject on when to return for screening results and for possible enrollment into the vaccination phase of the study.

7.1.2 Second Screening Visit (Day S2; Day 1 or Day 1 -4)—Phase 2

Subjects will have a second screening (S2) visit to verify their eligibility. Generally, the second screening visit and the first injection will occur on the same day. However, a 4-day window is allowed in case more time is needed. For each subject continuing with the screening process, the following activities will occur on Day S2:

1. The subject comes to the study clinic at the specified time. Study staff will confirm subject identity.

2. Laboratory and hepatitis serology results will be reviewed by a study clinician and with the subject. All results will be reviewed to confirm eligibility prior to conduct of further procedures. If a person is found to have a health issue during screening, the staff will advise them on how to get proper treatment.
3. For women able to become pregnant, a urine specimen will be collected for pregnancy testing.
4. Study staff will inquire about any new medical events since medical histories were recorded and confirm eligibility prior to conduct of further procedures.
5. A study clinician will perform a targeted physical examination (performed only if symptoms are present). Results will be reviewed by study staff and with the subject to confirm eligibility prior to conduct of further procedures.
6. If eligibility is confirmed, all information since the beginning of screening must be recorded on the study CRFs.

7.2 Screening: Phase 3 Subjects (S1/Day 1 or Day 1 -4)

Phase 3 subjects will sign one study consent before screening that covers both screening and study procedures. The investigator will record the screening IDs of all participants who enter screening; whether they entered the trial or failed screening, and the reason for screen failure on the screening/enrollment log. If a person is found to have a health issue during screening, the staff will advise them on how to get proper treatment.

For Phase 3 subjects, there is only one screening visit and it can occur on the same day as vaccination (Day 1), if the subject agrees. If not, the window for the screening visit allows Day 1 to occur up to 4 days after the screening visit.

After subjects are consented, the following activities will occur:

1. The subject will be interviewed to collect baseline demographic data.
2. A study clinician will interview the subject to collect a detailed medical history, focusing on current medical conditions. Study staff will review the information to confirm eligibility prior to conduct of further procedures.
3. A study clinician will perform a general physical examination. Results will be reviewed by study staff and with the subject to confirm eligibility prior to conduct of further procedures.
4. For women able to become pregnant, a urine pregnancy test will be done.
5. If eligibility is confirmed, all information since the beginning of screening must be recorded on the study CRFs.

7.3 Vaccination and Follow-up Periods: Phase 2 and Phase 3

7.3.1 First Vaccination (Day 1; S2 or S2 + 4 (Phase 2) or S1 or S1 + 4 (Phase 3))

Day 1 is the day of injection of the study product. For Phase 2 subjects, it can occur on Day S2 or up to 4

days after S2, if more time is needed for a potential subject to decide whether to join the study or if screening needs to be repeated. For Phase 3 subjects, it can occur the same day as screening or up to 4 days after, if the subject requires more time to consider vaccination. Note: The sites for blood draw and injection may be reversed if it is needed for proper injection and assessment of reactogenicity, or if the subject has a strong preference for the injection to be in the dominant arm.

1. If Day 1 is separate from S2 (or the screening visit for Phase 3), the study clinician must reconfirm subject identity and eligibility of the subject, including a urine pregnancy test for women who could become pregnant.
2. A study clinician will review the procedures for the vaccination study with each eligible subject. For Phase 2 subjects, a vaccine study ICF (ICF B) must be completed at this time (Phase 3 subjects have already signed the study consent). Upon entry into the trial portion of the study, the subject is assigned an ID number and may proceed to undergo further procedures related to administration of study product and evaluation of vaccine safety and immunogenicity.
3. A study clinician will perform a targeted physical examination (performed only if symptoms are present).
4. Prior to administration of study product, a serum specimen will be collected from the subject's dominant arm for anti-influenza serologic assays. This includes all subjects for Phase 2 and 1 of 3 clinical sites in Phase 3.
5. The subject will be administered one injection of study product in the deltoid of the non-dominant arm. (Injection may be given in the dominant arm if subject prefers.)
6. The subject will be observed for 30 minutes after administration in case of any immediate reactions. If the subject experiences an immediate adverse reaction, he/she will be treated and the event will be recorded on the CRF. A 30-minute Reactogenicity Assessment will be completed.
7. The subject will be given a Diary Card (and thermometer and ruler) in which the subject will be asked to record any local and/or systemic reactions that might appear from Days 1 to Day 7, and record any concomitant medications. The subject will be instructed how to use the Diary Card, thermometer and ruler. All relevant explanations should be included in the Diary Card. The Diary Card will also have contact information for the investigators, should the subject have any questions. The subject will be informed that a member of the investigator's team will visit or call the subject the next day (Day 2) and then call (or visit, if needed) 5 days after the injection (Day 6) to check on the subject's completion of the Diary Card and subject's well-being.
8. The subject will be instructed that if the subject later experiences an AE requiring medical care, the subject should inform the investigator as soon as possible and seek medical care as appropriate. If the subject visits a health care provider, the subject should be sure to inform the health care provider of participation in this study and provide the health care provider with the investigator's contact information.

7.3.2 First Week After Injection 1 (Day 1-7)

1. The subject will complete the Diary Card daily, reporting any local or systemic reactions experienced and medications taken from the evening of D1 through D7 after vaccination.
2. The subject will have been instructed that if he/she experiences an AE requiring medical care, the subject should inform the investigator as soon as possible and seek medical care as appropriate. If the subject visits a health care provider, the subject should be sure to inform the health care provider of participation in this study and provide the health care provider with the investigator's contact information.
3. At Day 2 post vaccination, a member of the investigator's clinical team will visit or call the subject to check that the subject is correctly completing the Diary Card and to check on the subject's well-being. At Day 6, the subject will be called (or visited, if needed) to again check on completion of the Diary Card and check on his or her status. *Note: For contact with the subject, calling is an acceptable alternative to home visit.*

7.3.3 Seventh Day after Injection 1 (Day 8 ± 2)

1. Study staff will confirm subject identity.
2. Study staff will review the subject Diary Card and interim history with the subject and inquire about any new medical events since medical histories were last updated. Any AEs that have occurred will be recorded in the appropriate section(s) of the CRF. Study staff will collect the Diary Card and keep it as a source document.
3. A study clinician will perform a targeted physical examination and record the information on the CRF. Results will be reviewed by study staff and discussed with the subject. Any AEs that have occurred will be recorded in the appropriate section(s) of the CRF.
4. **FOR PHASE 2 SUBJECTS ONLY:** If not done previously, the study clinician will review the results of the selected biochemical and hematological tests conducted from the blood drawn on S1 with the subject.
5. **FOR PHASE 2 SUBJECTS ONLY: Blood is collected for clinical safety laboratory testing** (ALT, creatinine, bilirubin, hemoglobin, and white cell and platelet counts). Specimen collection information must be documented on the CRF and in specimen collection forms.
6. The subject will be instructed that if the subject later experiences an AE requiring medical care, the subject should inform the investigator as soon as possible and seek medical care as appropriate. If the subject visits a health care provider, the subject should be sure to inform the health care provider of participation in this study and give the health care provider the contact information for the investigator.

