3.2.2 Safety Endpoints

The safety profile of IVACFLU-A/H5N1 will be evaluated by the proportion of subjects experiencing AEs, related or not related, of the following five categories for all subjects and by age group (18-40 years of age and 41-60 years age):

- Number and percentage of subjects with solicited local and systemic adverse events within 30 minutes after each vaccination.
- Number and percentages of subjects with solicited local adverse events (redness, swelling, pain, induration, and tenderness) over a 7-day period (Days 1-7; Days 22-28) post each vaccination.
- Number and percentages of subjects with solicited systemic/general adverse events (fever, fatigue/malaise, muscle aches (generalized), joint aches, chills, nausea, vomiting, and headache) over a 7-day period (Days 1-7; Days 22-28) post each vaccination.
- Number and percentages of subjects with unsolicited adverse events for 21 days post each vaccination.
- All serious adverse events (SAEs) occurring over the entire study period. (Days 1-91).

4 Study Design

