4. Blood specimens will be collected for immunological testing prior to vaccination. In Phase 2, blood specimens will be collected from all study participants (n=300). In Phase 3, blood specimens will be collected from approximately 300 subjects receiving the IVACFLU-A/H5N1 (vaccinees) among 500 enrolled at one of the three provinces, assuming equal enrollment.
5. Study product will be masked so that staff administering it and the subject are unaware of product allocation. The product will be administered and subjects will be carefully monitored for adverse reactions for 30 minutes after vaccination, with a completion of a 30-minute Reactogenicity Assessment.
6. During the first week (Days 1 to 7) following vaccination, subjects will be asked to record local and systemic signs and symptoms using preprinted Diary Cards, a thermometer, and a small ruler. Concomitant medications will also be recorded. In addition to solicited signs, subjects will be asked to report any other adverse events. Members of the investigator's clinical team will visit subjects on Day 2 and call them (or visit, if needed) on Day 6 to check that subjects are correctly completing the Diary Card, to check on the subjects' well-being, and remind the subject to return on Day 8. *Note: For contact with the subject, calling is an acceptable alternative to home visit.*
7. Subjects will return to the study clinic 7 days after injection of study product (on Day 8 +/- 2 days). At that time, the study staff will review the subjects' Diary Cards with them and transcribe all adverse events onto the case report forms. He or she will also do a targeted physical exam that focuses only on reported symptoms from the participant. For Phase 2 subjects only, blood specimens will be collected for clinical safety laboratory tests.
8. Two days before subjects are scheduled to receive Injection 2, subjects will be called to remind them of the next visit to the study clinic and to check on the subjects' well-being.

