14. On Day 91 (+/- 10 days) subjects will be contacted by phone for (a) closure of any ongoing AEs and concomitant medications; and (b) collection of any SAEs and new concomitant medications, if associated with the SAE reported. This will complete subject participation in the study and subjects will be exited from the study, however, if the subject reports any health problems, the PI may use his or her medical judgment and ask the participant to come to the clinic for an examination or any necessary testing.

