7.3.6 First Week After Injection 2 (Days 22-28)

1. The subject will complete Diary Card of any local or systemic reactions experienced; from the evening of D22 through D29 after vaccination.
2. The subject will have been instructed that if he/she experiences an AE requiring medical care, the subject should inform the investigator as soon as possible and seek medical care as appropriate. If the subject visits a health care provider, the subject should be sure to inform the health care provider of participation in this study and give the health care provider the contact information for the investigator.
3. At Day 23, a member of the investigator's clinical team will call the subject (or visit, if needed) to check that the subject is correctly completing the Diary Card and to check on the subject's well-being. At Day 27, the subject will be called (or visited, if needed) to again check on completion of the Diary Card, check on his or her status, and reminded of the study visit for the next day.

Note: For contact with the subject, calling is an acceptable alternative to home visit.

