7.3.10 Final Study Visit (Day 91; ± 10)

1. The subject will be contacted via telephone and identity confirmed.
2. Study staff will review interim medical histories and concomitant medications with the subject since these were last updated. The staff will seek the status of any AEs that were considered ongoing at the Day 43 visit. No new concomitant medication will be recorded unless it relates to a newly identified SAE.
3. Study staff will ask about any medical event that would constitute an SAE since the last visit. No new AE information will be recorded unless it qualifies as an SAE.
4. If an SAE is reported, the clinician should record the SAE on the appropriate form, notify the entities who require notification, and refer the participant for treatment of the SAE, if warranted.
5. After recording the information, the subject will be discharged from the study.

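### The visit windows allow the diary card to be collected before the 7-day solicited period ends, and allow the last SAE contact up to 10 days before Day 91

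*Protocol*

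**What the plan says.** Protocol 3.2.2 defines the solicited local and systemic endpoints "over a 7-day period (Days 1-7; Days 22-28) post each vaccination" and the SAE endpoint over Days 1-91. Both SAPs repeat these periods.

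Day 1 is the day of the first injection. Section 7.3.1, item 7, confirms the count: "5 days after the injection (Day 6". Section 7.3.2 has the first diary kept daily from the evening of Day 1 through Day 7.

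The card is taken at the next clinic visit. Section 4.6.3, item 7, sets that visit: "Subjects will return to the study clinic 7 days after injection of study product (on Day 8 +/- 2 days". Section 7.3.3 adds: "Study staff will collect the Diary Card and keep it as a source document". Section 7.3.7 uses the same window and the same instruction at Day 29.

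For the second diary, 7.3.5 gives Days 22-28, as does the heading of 7.3.6. Item 1 of 7.3.6 instead runs it "from the evening of D22 through D29 after vaccination". In item 3, subjects called on Day 27 are to be "reminded of the study visit for the next day", which would be Day 28.

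For the close of follow-up, 4.6.3, item 14, says "On Day 91 (+/- 10 days) subjects will be contacted by phone", and 7.3.10 ends with "After recording the information, the subject will be discharged from the study".

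**The concern.** The safety results will be reported as the percentage of subjects with a reaction over seven days after each injection, and as SAEs over Days 1-91. A two-sided window around a visit that closes a reporting period lets the visit fall inside that period. Subjects seen early then have a shorter daily record than subjects seen on time, yet they stay in the same denominator and have no protocol deviation. The final call raises the same issue, because discharge happens at the call whatever day it falls on.

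At stake is whether the reported percentages describe the stated periods for every subject, and whether the first and second injections are observed for the same length of time.

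**Working it through.** No sample size or power figure is involved. The check is calendar arithmetic: the permitted days are the nominal day ± the tolerance, and a visit is early if it falls on or before the last day of the period.

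1. **First diary** (3.2.2, 7.3.2, 7.3.3). Permitted days: 8 − 2 = 6 to 8 + 2 = 10. The period ends on Day 7, so Days 6 and 7 are early: 2 of 5.
   - Day 6 visit: Day 7 is lost (7 − 6 = 1 day; 1/7 = 14%). If the entry is made in the evening, Day 6 is lost too (2/7 = 29%).
   - Day 7 visit: at most the Day 7 entry is lost (1/7 = 14%).

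2. **Second diary, Injection 2 on Day 22** (7.3.5, 7.3.7). Permitted days: 27 to 31. The period ends on Day 28, so Days 27 and 28 are early: 2 of 5, with the same losses. If the diary runs through Day 29, as 7.3.6 item 1 says, it has 8 days. Then 3 of 5 permitted days are early, and a Day 27 visit loses 2 to 3 of 8 (25% to 38%).

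3. **Second diary, Injection 2 on another day.** The Table 2 header counts study days from Injection 1, while 7.3.7 and 4.6.3 item 11 describe this visit as 7 days after Injection 2. Section 4.6.3 item 9 allows Injection 2 at −2/+4 days; the heading of 7.3.5 says ±2. If the Day 29 visit is counted literally from Injection 1:

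| Injection 2 on | Seven-day period | Early visit days (of 27-31) |
|---|---|---|
| Day 20 | 20-26 | 0 of 5 |
| Day 22 | 22-28 | 2 of 5 |
| Day 24 | 24-30 | 4 of 5 |
| Day 26 | 26-32 | 5 of 5 |

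   If the visit is counted from the actual Injection 2, the result is 2 of 5 throughout.

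4. **Final call** (4.6.3 item 14, 7.3.10). Permitted days: 91 − 10 = 81 to 91 + 10 = 101, which is 21 days. Ten of them (81-90) come before Day 91, and Day 91 is itself the last day of the period. A Day 81 call leaves Days 82-91 uncovered: 10/91 = 11%. No later contact is planned. Section 9.4 continues follow-up after exit only for product-related SAEs that are still ongoing.

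5. **Missing-data rule** (Section III of both SAPs). A missing daily intensity takes the larger of the previous and the next recorded value. After early collection there is no next value, so at most the previous value is carried forward. A reaction that starts or worsens after collection is not recovered. Only a subject with all seven days missing is excluded, so a shortened diary counts as a full one.

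6. **Section 7.3.6 against the rest.** Diary end: Day 29 in item 1, against Day 28 in its own heading, 7.3.5, 3.2.2 and Table 2. Clinic visit: Day 28 by item 3, against Day 29 in 7.3.7 and Table 2.

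**The case against.** The other side has a good deal to say, and most of it limits the size of the point.

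- **Nominal dates.** Day 8 and Day 29 fall after the diary periods, and the Day 6 contact in 4.6.3 item 6 reminds subjects to return on Day 8. A reader might infer that the visits as planned cut the diary short. They do not; the windows only permit it.
- **Size of loss.** A flat 29% assumes a first-permitted-day visit and evening-only entries. Section 7.3.2 asks for daily entries and ties the evening only to the start. These are also shares of diary days, whereas the endpoint is the percentage of subjects with a reaction. Only a first onset or a worsening in the missing days changes it.
- **Classification.** A reader might infer that a reaction starting on Day 6 or 7, after collection, is neither solicited nor unsolicited. The documents do not support that. Section 9.2.6 classifies by onset, so it remains solicited. Section 8.1.2 has solicited signs recorded throughout participation, with clinician evaluations on Days 22 and 43 among others. Sections 7.3.5 and 7.3.9 review interim history, and Section VIII of both SAPs accepts reactions seen by staff or reported. The event can still be captured, but by recall and not as a daily graded record.
- **Bias between arms.** Allocation is randomised and blinded and the windows are the same in every arm. None is shown.
- **Later calls.** The final window also extends to Day 101, so some subjects are followed past Day 91. This does not fill the gap for those called early.

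What stands is that in-window visits can shorten the record, neither SAP restores the missing days, and 7.3.6 is inconsistent.

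**Conclusion.** The point holds as a statement about what the windows permit. Two of five permitted days at each diary visit fall before the solicited period is complete, and a visit on the earliest of them costs about 1 to 2 of 7 diary days. Ten of 21 permitted days for the final call precede Day 91, with up to 10 of 91 days (11%) left without planned contact.

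The figures for the second diary assume Injection 2 on Day 22, or a visit counted from the actual injection. They can be worse if Day 29 is counted from Injection 1 and Injection 2 is given late within its window.

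The documents do not say how often visits would be early, so under-counting is possible but not demonstrated. The consequence is incomplete absolute 7-day and Days 1-91 incidences and weaker comparability between the first and second injection, not a distorted comparison of vaccine with placebo. The conflict within 7.3.6 is a separate drafting matter and needs correction whatever view is taken of the windows.

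**What to change.** 1. Make both diary visits late-only and count them from the actual date of the preceding injection: 7 days after injection, 0/+2. A fixed Day 29 (0/+2) window is not enough: with Injection 2 on Day 24 the period ends on Day 30, so visits on Days 29 and 30 would still be early.
2. State that a card is not collected until its seventh-day entry is complete.
3. Make the final call late-only (Day 91, 0/+10), or add a contact on or after Day 91 whenever the call was early.
4. Reconcile 7.3.6 with the Days 22-28 period and the Day 29 visit.
5. Reconcile the two Injection 2 windows in 4.6.3 item 9 and the heading of 7.3.5, and state which injection the later study days are counted from.

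The cost is protocol wording and somewhat tighter scheduling: three permitted days instead of five at each diary visit, and 11 (Days 91-101) instead of 21 for the final call, unless the extra contact is preferred.
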